In general, we approach this study as a pragmatic clinical trial, such that we intend to maximize inclusion to reflect actual clinical practice and to demonstrate effectiveness, rather than efficacy, of the intervention. Inclusion criteria include: (1) having a primary care provider at VA Boston PCC; (2) having a positive screen on the AUD-C; (3) drinking above CDC guidelines in the past 30 days; (4) willing to provide us with at least 1 "locator person" (and preferably 2 locator persons) who always knows their whereabouts (explanation on p. 5). Exclusion criteria are: (1) Veterans who do not have a valid telephone number and mailing address, and who expect to move in the next 6 months. This information is needed to ensure 3-month follow-up contact and completion of Aim #3; (2) Veterans who report less than 14 drinks per week or less than 5 drinks on any one occasion in the past 30 days when screened on the Quick Drink Screen (described in Measures). The purpose of adding this screening is to account for the fact that the AUD-C measures Veterans' alcohol consumption over the past year, and it is possible for Veterans to screen positive on the AUD-C but to have stopped drinking

during the past 30 days. We will use the Quick Drinking Screen (see Measures) to exclude these Veterans who screen positive on the AUD-C but are not consuming unhealthy quantities of alcohol at the time of the study, because the primary study outcomes include quantitative measures of alcohol consumption. These Veterans may not be currently in need of brief intervention because they have recently cut down their drinking. (3) Veterans who have participated in substance abuse treatment in the past 30 days because they are already receiving care.

The table below summarizes the eligibility criteria.

We note that the study will not exclude patients with mental illness, traumatic brain injury, or other mental or neurological conditions. Second, we will measure health literacy to ensure the program can be used by any Veteran, no matter their familiarity with health issues.

Study Eligibility Criteria	
Inclusion Criteria	Exclusion Criteria
AUD-C \geq 5	Participation in Aim 1 of the study
Receive primary care where recruited	Drank <14 drinks/wk and <5 drinks on one occasion in past 30 days
Drinking more than guidelines in past 30 days	Unsure of phone and address over next 6 months
Stable phone and address over next 6 months	Alcohol treatment in last 30 days

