Supply at least 1 (up to 2) locator person(s)	Unwilling to supply locators.

Measures

The study measures will be derived from data collected at the interviews, as well as from the VA's computerized patient record system, CPRS. The measures are summarized in the table below and attached in Appendix A. Data will be entered into REDCap, a free, secure Web application that facilitates the collection and entry of research data. User-friendly electronic data capture (EDC) tools enable users to quickly develop surveys and databases from conception to production on the Web without additional software requirements. This tool helps researchers enter, store, and manage their project data in a systematic manner. REDCap is a VA Intranet Web application; surveys can only be administered to respondents while logged into the VA Intranet.

Research Measures and Schedule of Use

Measures	Screening	Baseline	Session 2 (intervention group only)	3 Month Follow-up
AUD-C (from health technician)	X			
Quick Drink Screen	X			X
Demographics and other		X		
REALM-SF (health literacy)		X		
MINI-Alcohol		X		
SIP		X		X
System Usability Scale			X	
ECA Questionnaire			X	
Satisfaction with alcohol treatment in primary care (1 item)				X
CPRS data extraction				X

Demographics and other. Age, gender, ethnicity, branch of military service, and other descriptors or questions of relevance to this study (e.g., previous substance abuse treatment) are included. See Appendix A for document.

Quick Drink Screen (QDS). The QDS will be used to assess quantity and frequency of drinking over the past 30 days. When compared with the Timeline Followback over a one-year period, intra-class correlations on all five variables ranged between 0.66 and 0.82, which indicates that the QDS may be an expedient way of gathering summary drinking data.

Rapid Estimate of Adult Literacy in Medicine—Short Form (REALM-SF). The REALM-SF is a 7-item word recognition test that provides a valid and quick assessment of health literacy.

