Alcohol use and related behaviors will be assessed by in-person survey at baseline and by telephone survey at 3 months after randomization. Principal intervention effect analyses will be performed at 3 months. The primary dependent (outcome) variables are number of drinking days per week (frequency) and average drinks per drinking day (quantity). Secondary dependent variables are percent receiving brief intervention and percent referred for further evaluation or treatment of alcohol problems.

Independent Variables

The two independent variables are the experimental condition, Treatment as Usual vs. Treatment as Usual plus Relational Agent Intervention, and the severity of alcohol use, dichotomized as Risky Drinking vs. Alcohol Use Disorder. The experimental condition will be assigned by random allocation (see Section 4.e.7).

The severity of alcohol use variable, which will be used to allocate Veteran-participants into two strata prior to randomization, will be ascertained by the baseline completion of the MINI.

Dependent Variables

The primary dependent variables (i.e., the main study outcome measures) are **number of drinking days per week** and **average drinks per drinking day**. Because the Relational Agent will target reduction of both the frequency (number of drinking days per week) and the quantity (average drinks per drinking day) of alcohol consumption, each of these measures will be considered separately as primary outcome measures. These variables are measured by the QDS.

Secondary dependent variables include **completion of brief intervention** (yes/no) and **referral for evaluation/treatment** (yes/no); these secondary dependent variables will be ascertained from review of CPRS. We will also ascertain completion of brief intervention and referral for evaluation/treatment from the interviews with participants; we will assess concordance between CPRS and Veterans' self-report and, for main analyses, we will count brief intervention or referral as completed if they are ascertained from either source.

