Other variables that we will use to describe the sample and explore in cross-tabulations with the outcome variables include summary scores from the REALM health literacy questions and .the ECA Questionnaire.

Statistical Analysis

The figure below shows a schematic representation of the research design. For visual clarity, it does not show the descriptive variables mentioned above.

Preliminary Analyses: In preliminary analyses, we will examine the distributions of all dependent variables, and consider appropriate transformations. In particular, we will consider an arcsine transformation (appropriate for reported proportions) for the “number of drinking days per week” and a log transformation (appropriate for highly skewed distributions) for “average drinks per drinking day”. The 4 groups will be tested for any differences in socio-demographic variables. All quantitative variables (e.g. Age) will be tested by 2-way between groups Analysis of Variance (ANOVA); all qualitative variables (e.g. Gender) will be tested by 3-dimensional Chi Square (Mantel-Haenszel test). Any variable found to be significant will be entered into all subsequent analyses as a covariate.

Checks for “non-Response” Bias: The potential for differential drop-out rates among the four groups is itself an interesting and important empirical question, with clinical implications. Drop-out rates will be tested by Chi Square. Factors that may contribute to drop-out rate will be tested by logistic regression. In effect, the four groups can be stratified at Baseline into Completers and non-Completers. Then, these groups will be compared on Baseline values to determine which, if any, are significant systematic “predictors” of Completion.

Statistical Analyses: If there is no significant differential drop-out rate attributable to Alcohol Group, to Treatment Group, or, especially, to Alcohol x Treatment interaction, then the non-completion rate can be considered as a random loss, and Completers as a representative sample. In that case, the dependent variable(s) will be tested by 3-way mixed design AN(CO)VA. If it is determined that there is a differential drop-out rate such that the data are not missing completely at random (NMCAR), then we will utilize a generalized estimation equation (GEE) approach, which should provide an unbiased estimate of the intervention effect.

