GEE utilizes inverse probabilities to correct for any bias associated with NMCAR, with participants who are Completers weighted with the drop-out probabilities of participants with the “same” characteristics at Baseline. These weighting values will be estimated from the logistic analyses described above.

The overall design is a three-way mixed-design with Treatment Arm (Treatment as Usual vs. Treatment as Usual plus Relational Agent Intervention) and Drinking Severity (Risky vs. Alcohol Use Disorder) and 2 occasions (0 and 3 months) as the repeated measures design. We will take an intent-to-treat approach to the analysis; Veterans will be included in our primary analyses regardless of their level of adherence with their assigned intervention. Participants who do not complete the 3-month follow-up assessment will be considered to have missing data for that assessment and will not be included in the analysis of intervention effectiveness. The secondary outcomes, which will be “incidence rates”, will be tested by logistic regression.

Primary Hypothesis: The Relational Agent will be more effective than Treatment as Usual in reducing the quantity and frequency of alcohol use.

Our primary analyses of the effectiveness of Treatment as Usual vs. Treatment as Usual plus Relational Agent Intervention will focus on measurement outcome variables at the **3-month follow-up**. Separate analyses will be performed for the two primary outcome measures: number of drinking days per week (frequency) and average drinks per drinking day (quantity), both reported over a month. Here we describe the analytic approach for the outcome of quantity of alcohol use (average drinks per drinking day); the approach for frequency will be analogous. Initially our analysis will be through analysis of covariance models. We will include baseline values of the outcome variable as a covariate in these models, so our analyses may be interpreted as focusing on the change in outcome from baseline to three month follow-up. If any key characteristics of our sample were found to differ between groups, we will enter those as covariates as well.

Secondary Hypothesis: The Relational Agent will be more effective than Treatment as Usual in improving rates of brief intervention.

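### Does the plan leave average drinks per drinking day without a usable value for a Veteran who has stopped drinking by 3 months?

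*Combined protocol and SAP*

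**What the plan says.** The Study Design for Aim 2 section names the two primary outcomes: "The primary dependent (outcome) variables are number of drinking days per week (frequency) and average drinks per drinking day (quantity"). The Dependent Variables section treats each as a primary outcome in its own right and takes both from the Quick Drink Screen (QDS). The Measures section gives the recall window: "The QDS will be used to assess quantity and frequency of drinking over the past 30 days". It places the instruments themselves in Appendix A, which is not part of the available text. Under Primary Hypothesis the outcomes are described as "average drinks per drinking day (quantity), both reported over a month", and the model is an analysis of covariance at 3 months with the baseline value as covariate.

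Three other statements bear on the point:

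- **Scale.** Under Preliminary Analyses, "we will examine the distributions of all dependent variables, and consider appropriate transformations". For quantity the candidate is "a log transformation (appropriate for highly skewed distributions"). No offset is named and the log is not adopted.
- **Who is analysed.** Under Statistical Analysis, "Veterans will be included in our primary analyses regardless of their level of adherence with their assigned intervention".
- **Who is missing.** In the same paragraph, "Participants who do not complete the 3-month follow-up assessment will be considered to have missing data for that assessment". No other category of missing outcome is defined.

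At entry, the Eligibility Criteria require "drinking above CDC guidelines in the past 30 days", so every screening value of the ratio is above 0.

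**The concern.** A ratio per drinking day has no value when there are no drinking days. Entry rules keep such people out at baseline, but nothing keeps them from appearing at 3 months. Stopping drinking is a plausible response to an intervention against drinking, especially as the Sample Size section expects two-thirds of the sample to have an alcohol use disorder.

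If these Veterans are scored 0, a plain log cannot be taken. Software would return a missing value and silently drop them. That would remove randomised completers because of their outcome, and the arm in which more people stopped drinking would lose its best results. If an offset is added instead, its size affects the answer. Since quantity is judged on its own as a primary outcome, an unwritten rule could in principle sway a primary conclusion.

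**Working it through.** **1. The plan's own power figures.** The Sample Size section gives power of 0.84, 0.82 and 0.78 for 72, 68 and 63 completers per arm, a medium effect and alpha 0.05. Taking medium as d = 0.5 (an assumption, since no number is printed) and a two-sided two-sample t test with noncentrality d × √(n/2), power is 0.846, 0.825 and 0.795. These agree with the table to within 2 points. The table assumes that every completer has a value.

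**2. Which reading the text supports.** There are three ways to handle a completer with no drinking days.

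| Handling | Fit with the Statistical Analysis section |
|---|---|
| Score 0 and keep | Consistent: the person completed the assessment, so is not missing |
| Treat as missing | Inconsistent: only non-completers are missing |
| Drop through a plain log of 0 | Inconsistent for the same reason, and visible as a fall in N below the number of completers |

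Only the first fits. It also matches the frequency outcome, where the same person scores 0 drinking days without difficulty and the arcsine under consideration accepts 0.

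**3. What dropping abstainers would do.** This is the contrast that the gap itself concerns.

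- *Power.* With a share a excluded equally from both arms, normal-approximation power is Φ(0.5 × √(72(1 − a)/2) − 1.96). This gives 0.851 at a = 0, 0.812 at a = 10% (64.8 per arm) and 0.765 at a = 20% (57.6 per arm).
- *Estimate.* Suppose drinkers in both arms have mean 6 and SD 4, with 5% abstinent under usual care and 15% with the agent. Dropping abstainers gives a difference of 0. Scoring them 0 gives 6 × (0.95 − 0.85) = 0.6 drinks. The variances are 0.95 × 52 − 5.7² = 16.91 and 0.85 × 52 − 5.1² = 18.19, so the pooled SD is √17.55 = 4.19 and d = 0.6/4.19 = 0.14.

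So exclusion would matter, but it is the handling that the plan's own rules rule out.

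**4. What the choice of scale does once abstainers score 0.** Simulation, 3,000 trials per row, 72 per arm. Drinks per drinking day is log-normal with median 7 and log SD 0.6; baseline correlation is 0.5; two-thirds are in the alcohol use disorder stratum. Analysis of covariance uses baseline on the same scale and stratum, at two-sided 0.05. Entries are the percentage of trials significant in favour of the agent.

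| Abstinent, usual care / agent | Effect in continuing drinkers | Raw | log(x+1) |
|---|---|---|---|
| 5% / 20% | none | 29 | 66 |
| 10% / 20% | none | 16 | 31 |
| 10% / 20% | 0.25 log reduction | 81 | 78 |
| 5% / 10% | 0.25 log reduction | 76 | 75 |
| 2% / 5% | 0.25 log reduction | 76 | 79 |
| 10% / 10% | 0.25 log reduction | 56 | 35 |
| 0% / 0% | 0.25 log reduction | 71 | 81 |

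The two scales are within 3 points when drinking and abstinence both improve. They part when abstinence is the only effect (log better) or is equal in the arms (raw better). With no abstainers at all they still differ by 10 points, and they give different verdicts on the same data in 13% of trials; at 2% / 5% the figure is 12%. Part of the disagreement is therefore the ordinary cost of choosing a scale. Either scale, fixed in advance, holds its error rate (4.7% to 5.7% simulated under no effect).

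**5. Whether looking at the distribution helps.** With 10% abstinent in both arms, mean skewness is +1.7 raw and −0.8 for log(x+1). The plan's criterion, skewness, usually separates these two. A near tie needs a much smaller offset such as 0.1 (skewness −1.9), which the documents never mention.

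**6. How many people.** Of the 126 to 144 completers expected, 5% is 6.3 to 7.2 and 10% is 12.6 to 14.4.

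**The case for a change.** The strongest case for a change is that zero-day reports are foreseeable. The Eligibility Criteria already recognise that a screen-positive Veteran may have stopped drinking, yet only the entry stage is dealt with. Calling 0 the natural value does not finish the matter either, because 0 has no logarithm: an analyst who prefers the log must name an offset, and log(x+0.1) behaves differently from log(x+1) (18% against 35% power with 10% abstinent in both arms and a 0.25 reduction). If the scale were picked after seeing results, taking the smallest of three p-values would give a false-positive rate of 8.2% to 8.9%. Writing a rule down would cost a sentence.

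What stands is that the rule is unwritten in the available text and that dropping abstainers would be wrong. The rest is weaker. The false-positive figure is an upper bound for a practice that the plan does not describe; it ties the transformation to the shape of the distribution. The offset matters only if the log is adopted with zeros present, and the planned examination would show those zeros before the scale is settled. The simulated gaps all score abstainers 0, so they measure the choice of scale and not the missing value. The largest gap comes from one scenario, in which abstinence quadruples while continuing drinkers do not change. The Hypotheses section's description of quantity as drinks per day is a loose phrase: the design, analysis and sample size sections all use the per-drinking-day definition.

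**Conclusion.** No change to the plan follows. The value of the quantity outcome at zero drinking days is a gap in detail that an analyst following the stated intent-to-treat approach and missing-data rule would fill in one way: score 0 and keep the Veteran in the analysis. The log is a candidate to be weighed after inspection, so its failure at 0 is a limit the team would meet and handle then. The choice between raw and log(x+1) is a fair trade-off. Under the assumptions shown, each scale wins in some scenarios, by up to 37 points for the log and 21 for the raw scale (56 − 35), with nearly equal results where drinking and abstinence both improve.

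This rests on two things. The abstinence rates, drinking distribution and effect sizes are assumptions, because the documents give none. Appendix A was not available: a scoring rule there would close the point outright, but the conclusion does not depend on finding one. The frequency outcome and the printed power table are unaffected.

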The primary hypothesis is that 1) the Relational Agent will be more effective than TAU in reducing the quantity (drinks per day) and frequency (number of drinking days per week) of alcohol consumption.

The two secondary hypotheses are that 2) the Relational Agent will be more effective than TAU in improving rates of brief intervention; and 3) the Relational Agent will be more effective than TAU in improving rates of referral. Additional exploratory hypotheses are listed in the Analysis section.

(2) Background, Significance, and Relevance to Veteran's Health

Please see Aim 1 protocol and grant proposal.

(3) Work Accomplished

Please see grant proposal for pilot work. So far in this study we have completed part of Aim 1. We interviewed 20 veterans and collected information on their preferences for the appearance of the relational agent, as well as some information on how the setting should look. We are in the process of collecting feedback on the sections of the relational agent program that we have programmed so far and making final adjustments to the program.

(4) Work Proposed

Methods

Setting and Population

We will recruit a total of 180 Veterans from primary care clinics, both men and women. We expect to recruit approximately 10-40 participants per month over 11 months, finishing the 3 month follow-up visits in 14 months from the start of recruitment. The study will be conducted first in the Jamaica Plain primary care clinic (JP-PCC) of the VA Boston Healthcare System. If we are unable to meet our recruitment goals, we will also attempt to recruit at the West Roxbury primary care clinic (WRX-PCC) or Brockton primary care (BR-PCC). In any case, we will exclude the veterans who participated in Aim 1.

Recruitment

We are working collaboratively with the team leaders and clinic staff to identify a process by which Veterans who screen positive on the AUD-C can be referred to the research assistants without disruption to the workflow of primary care encounters. The usual practice in this setting is that the health technician or LPN administers the AUD-C and informs the physician if the Veteran has a positive screen. The physician (or other responsible primary care clinician) is then responsible for delivering the brief intervention. Per current practice, referral to Mental Health for alcohol problems is routinely made by computerized order to one of the specialty substance abuse clinics.

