Power considerations focus on our primary hypotheses, which examine intervention effects on two primary outcomes, drinking days per week and average drinks per drinking day, at 3 months follow-up. For our principal analyses we will separately examine effects on these outcomes at 3 months through analysis of covariance, controlling for baseline levels of the outcome variable. Reported effects of brief intervention vary in the literature.

For instance, a meta-analysis by Moyer et al. found an effect size for alcohol consumption in non-treatment-seeking samples of 0.67 for drinks per day at three months, but it quickly drops to 0.14 at six months, and 0.24 at 12 months.⁹⁵ On the other hand, Bien et al. reported an average effect size of 0.64 at 12 months for the reduction in drinks per month, but it varied in studies they reviewed from 0.27 to over 1.0.¹⁷ More to the point for our study, Riper et al.⁹⁶ conducted a meta-analysis of web-based brief interventions and reported a medium effect size ($d=0.44$). There are little data to suggest that those with alcohol use disorders derive more or less benefit from brief intervention.³³ However, VA clinical guidelines suggest that people with alcohol use disorders need to be referred to specialty treatment, implying that they might not be expected to benefit solely from brief intervention. With these prior studies in mind, and with the explicit design of this study as an initial, single-site RCT to assess the potential effectiveness of the Relational Agent Intervention on frequency and quantity of alcohol use among Veterans, we have powered the trial for the detection of a large effect size, as defined by Cohen.⁹⁷

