We begin our sample size estimation with the observation that 5,571 underwent AUD-C screening in our study setting during fiscal year 2010. We estimate that $1.25 * 5,571 = 6,963$ will be screened during the **15-month** study enrollment period. National samples indicate that about 20% of Veterans screened receive a positive score on the AUD-C,²⁶ which would be consistent with the estimated prevalence in the larger population. Therefore, $6,963 * 0.2 = 1,393$ Veterans will be potentially eligible. Because of clinic workflow and research assistant availability, we anticipate approaching approximately **500** of these Veterans. Based on [name] pilot study of a Relational Agent to screen for alcohol problems in primary care (described above, Section 4.a.1) and the two recently completed pilot studies of the Relational Agent in the Primary Care Clinic of VA Boston, we estimate that **36% of the 500** Veterans approached, or **180** Veterans, will agree to participate. We estimate that these **180** Veterans will be distributed in a 2:1 ratio as those with alcohol use disorders ($N=120$) and those with risky drinking ($N=60$), based on studies in VA.

Rates of attrition, or loss-to-follow-up, in prior studies of brief intervention for alcohol problems have typically ranged from 10% to 30%. Based on our familiarity with following up study participants in alcohol and substance abuse interventions, and particularly noting our use of financial compensation for participation, we anticipate that our loss-to-follow-up will be on the lower end of this range. However, in the table below we show power estimates for three possible rates of loss to follow-up: 20%, 25% and 30%. Table 5 shows estimated power to detect a **medium (Cohen's) effect size**, at an alpha level of 0.05, given the three possible rates of loss-to-follow-up.

Power estimates for a range of loss-to-follow-up rates

% Loss-to-Follow-Up	Experimental Group	Alcohol Use Disorders (N)	Risky Drinking (N)	Total (N)	Power
20%	TAU	48	24	72	0.84
	TAU+RAI	48	24	72	
25%	TAU	45	22.5	68	0.82
	TAU+RAI	45	22.5	68	
30%	TAU	42	21	63	0.78
	TAU+RAI	42	21	63	

Note: TAU=Treatment as Usual; RAI=Relational Agent Intervention.

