Thus, for our primary outcome, we estimate that we will have more than 80% power to detect a medium effect of the intervention with loss-to-follow-up rates approaching 30%. We will monitor loss-to-follow-up closely and, if we discover that the attrition rate is exceeding 30%, we will increase our sample size to account for the loss-to-follow-up.

We will recruit a total of **180** Veterans from PCC, with approximately **60** participants in the Risky Drinking Group and **120** participants in the Alcohol Use Disorders Group. Accounting for 20-30% loss to follow up we expect that at least **126 to 144** Veterans will complete the 3-month follow-up.

Specific Aim 3: Examine in-depth Veterans' experience with the Relational Agent Intervention.

Because this Aim is exploratory in nature, there are no associated hypotheses. Following the RCT, we will conduct a formative evaluation (Aim 3), with in-depth interviews, to characterize the elements of the Relational Agent Intervention that Veterans prefer, and the features that emerge as most effective and those that seem extraneous or even counter-productive.

Rationale for formative evaluation

Formative evaluation will inform future evaluation and implementation efforts, specifically in the area of Relational Agents for alcohol problems and more generically for interventions using health information technology to engage Veterans in their care in the primary care setting. Formative evaluation is valuable in the context of an intervention that results in quantitative improvement of outcomes because it can yield information regarding those characteristics of the intervention that seemed most useful and effective from the perspective of the study participants. Perhaps more importantly, formative evaluation is crucial in the context of an intervention that does not result in quantitative improvement in the target outcome (i.e., in the setting of a "negative study"), because it can identify the factors that may have prevented an otherwise-potent intervention from achieving the intended outcome.

In-depth Interviews

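### Two primary drinking outcomes are tested separately with a single undivided 0.05 and no rule on whether one or both must succeed

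*Combined protocol and SAP*

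**What the plan says.** The Dependent Variables part of Study Design for Aim 2 names two primary outcomes, drinking days per week and average drinks per drinking day, and states that "each of these measures will be considered separately as primary outcome measures". The Primary Hypothesis part of Statistical Analysis agrees: "Separate analyses will be performed for the two primary outcome measures". Each is to be analysed by ANCOVA with its baseline value as covariate.

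The claim that these analyses should support is worded differently from place to place:

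- Hypotheses or Key Question gives one primary hypothesis, about "reducing the quantity (drinks per day) and frequency (number of drinking days per week) of alcohol consumption".
- Statistical Analysis again gives one: "The Relational Agent will be more effective than Treatment as Usual in reducing the quantity and frequency of alcohol use".
- Sample Size and Power Considerations uses the plural: "Power considerations focus on our primary hypotheses, which examine intervention effects on two primary outcomes".
- The conclusion under the power table speaks of a single outcome: "Thus, for our primary outcome, we estimate that we will have more than 80% power to detect a medium effect of the intervention", with loss to follow-up approaching 30%.

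The only significance level is in the power section, which introduces its table as power for a medium effect "at an alpha level of 0.05, given the three possible rates of loss-to-follow-up". The analysis sections give neither a level nor sidedness. The documents contain no adjustment, alpha split, testing order or one-or-both rule. The power section also says "we have powered the trial for the detection of a large effect size", although its table and conclusion refer to a medium effect.

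**The concern.** Two separate primary tests under one hypothesis leave three readings open.

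1. Success on either outcome supports the hypothesis.
2. Both outcomes must succeed.
3. Each outcome carries its own claim.

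Under the first and third, two tests at the full 0.05 give more than a 5% chance of at least one false positive. Under the second, that error is controlled, but the power that matters is the power to win on both.

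The practical stake is a split result. If one outcome reaches significance and the other does not, the plan does not say whether the primary hypothesis is supported. The reading could then be chosen after the results are known.

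**Working it through.** **Inputs from the documents.** Two primary outcomes; alpha 0.05; 180 randomised; completers per arm 72 / 68 / 63 at 20 / 25 / 30% loss (the 25% row is 67.5, rounded); stated power 0.84 / 0.82 / 0.78; effect described as medium.

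**Assumptions.** d = 0.5 for a medium effect and d = 0.8 for a large one; two-sided testing; correlation r between the two test statistics; correlation b between baseline and follow-up. The documents give none of these values, so ranges are shown.

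**Step 1: reproduce the power table.** Two-sample t test, noncentrality d × √(n/2), df 2n − 2. For d = 0.5 the noncentrality is 0.5 × √36 = 3.00, 0.5 × √34 = 2.92 and 0.5 × √31.5 = 2.81.

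| Loss | n per arm | Stated | d = 0.5 | d = 0.8 |
|---|---|---|---|---|
| 20% | 72 | 0.84 | 0.846 | 0.998 |
| 25% | 68 | 0.82 | 0.825 | 0.996 |
| 30% | 63 | 0.78 | 0.795 | 0.994 |

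The table is reproduced to within 2 points as power for one outcome at two-sided 0.05 and d = 0.5. One-sided 0.05 gives 0.912 / 0.898 / 0.877 (normal approximation: 0.851 / 0.830 / 0.801 two-sided) and does not fit. A large effect does not fit either. The table makes no allowance for a second primary test.

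**Step 2: chance of at least one false positive, each outcome at 0.05.** At r = 0 this is 1 − 0.95² = 0.0975, and 1 − 0.975² = 0.0494 counting false claims of benefit only. Other values are from the bivariate normal.

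| r | Two-sided | Benefit direction only |
|---|---|---|
| 0 | 9.75% | 4.9% |
| 0.5 | 9.1% | 4.5% |
| 0.7 | 8.4% | 4.2% |
| 0.9 | 7.0% | 3.5% |

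For one test the figures are 5% and 2.5%.

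**Step 3: joint power, true d = 0.5 on both.** At r = 0 without baseline adjustment it is the square of the single-outcome power: 0.846² = 0.716, 0.825² = 0.681, 0.795² = 0.632. Other entries are from simulated correlated t statistics. ANCOVA is represented by an effective d of 0.5/√(1 − b²), which is 0.524 at b = 0.3 and 0.577 at b = 0.5, with df 2n − 3. Ranges run from r = 0 to r = 0.7.

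| Analysis | 20% loss | 25% loss | 30% loss |
|---|---|---|---|
| No baseline adjustment | 0.72–0.77 | 0.68–0.75 | 0.63–0.71 |
| ANCOVA, b = 0.3 | 0.77–0.82 | 0.74–0.79 | 0.69–0.75 |
| ANCOVA, b = 0.5 | 0.87–0.89 | 0.84–0.87 | 0.80–0.84 |

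**Step 4: exactly one outcome significant, same truth.** At r = 0 without adjustment it is 2 × power × (1 − power); for example, 2 × 0.846 × 0.154 = 0.26. Ranges run from r = 0.7 to r = 0.

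| Analysis | 20% loss | 25% loss | 30% loss |
|---|---|---|---|
| ANCOVA, b = 0.5 | 8–13% | 9–15% | 11–19% |
| ANCOVA, b = 0.3 | 13–21% | 14–24% | 16–28% |
| No baseline adjustment | 15–26% | 16–29% | 18–33% |

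**Step 5: power per outcome under Holm.** The smaller p-value is compared with 0.025 and, if it passes, the larger with 0.05. Without baseline adjustment, for r = 0.7 to 0, power per outcome is 0.813–0.828 / 0.788–0.803 / 0.753–0.768. Against 0.846 / 0.825 / 0.795, the loss is about 2 to 4 points.

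**The case against.** The strongest defence is that the plan treats the outcomes as two separate questions. It uses *separately* or *separate* in the design, analysis and power sections, and the power section refers to hypotheses in the plural. On that view each outcome carries its own claim, the tabulated power is the right one, and whether two separately reported claims need family-wise control is a matter of judgement, particularly in what the plan calls an initial single-site trial. The outcomes are also likely to be correlated, which reduces the error.

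Part of this stands. The power table is sound for either outcome alone, and separate claims are a defensible position. But the plan does not adopt it: it twice states one primary hypothesis covering both outcomes. It labels other analyses exploratory, but not these. Correlation helps only in part, since the error is still 7.0% at 0.9.

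It is also fair that split-result rates should not rest on an unadjusted comparison when ANCOVA is planned. With a useful baseline correlation the rates are roughly halved, but they do not become negligible.

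A reader might infer that the trial is underpowered for its primary hypothesis. The documents do not support that. It would require that both outcomes must succeed and that the baseline correlation is weak, and they establish neither. At an assumed baseline correlation of 0.5, joint power is at least 0.80 in every row.

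**Conclusion.** The gap is real and should be fixed. Followed as written, two primary tests at an undivided 0.05 give a 7.0% to 9.75% chance of at least one false positive over assumed correlations of 0.9 to 0, unless both outcomes are required. A split result has no stated interpretation. These sizes rest on assumed correlations, and the split rates also on d = 0.5 for both outcomes.

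It would go too far to say that the type I error is inflated outright: that depends on a rule the plan does not give. It would also go too far to call the power table wrong. It lacks a statement that it applies per outcome, and its two-sided 0.05 and d = 0.5 are inferred from its figures.

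The reference to a large effect is a separate wording error in the same section. Only a medium effect reproduces the table, so it does not show that the calculation was done for a large one.

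**What to change.** Before outcome data are examined, state the success rule and make Hypotheses or Key Question, the Primary Hypothesis text, the opening of the power section and its conclusion agree with it.

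- **Either outcome can support a claim (default): Holm at overall two-sided 0.05.** The cost is the 2 to 4 points per outcome shown above. With d = 0.5 on both and no baseline adjustment, at least one outcome succeeds with probability 0.81 to 0.95 across the three loss rates (assumed correlation 0.7 to 0).
- **Alternative: a named fixed order.** The first outcome keeps the tabulated power. The second outcome's power becomes the joint power, 0.63 to 0.77 without baseline adjustment.
- **Both required.** Say so, keep 0.05 for each, and report joint power with its assumed between-outcome and baseline correlations.

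The table label and the power sentence beneath it must follow the rule chosen. A per-outcome label at 0.05 is correct only if each outcome is tested at the full 0.05. Under Holm without baseline adjustment, a claim of more than 80% power does not hold at 30% loss, where the table itself already shows 0.78, and is borderline at 25% (0.79 to 0.80).

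The sponsor should confirm that the table used two-sided 0.05 and d = 0.5. Replace *large* with *medium* in the power section. All of this is wording and labelling; no additional participants are needed.
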